#### **13.1.2.2 Documentation of Serious Adverse Events**

All SAEs that occur after obtaining informed consent and assent (where applicable) through the Safety Follow-up Visit, regardless of causality, will be reported by the investigator to Vertex GPS. In addition, all SAEs that occur after the Safety Follow-up Visit and are considered related to study drug(s) will be reported to Vertex GPS **within 24 hours**.

SAEs will be recorded on the Vertex Organized Safety Information Collection Form (hereafter referred to as the “SAE Form”) using a recognized medical term or diagnosis that accurately reflects the event. SAEs will be assessed by the investigator for relationship to the investigational study drug(s) and possible etiologies. On the SAE Form, relationship to study drug(s) will be assessed only as related (includes possibly related) or not related (includes unlikely related), and severity assessment will not be required. For the purposes of study analysis, if the event has not resolved at the end of the study reporting period, it will be documented as ongoing. For purposes of regulatory safety monitoring, the investigator is required to follow the event to resolution and report to Vertex the outcome of the event using the SAE Form.

#### **13.1.2.3 Reporting Serious Adverse Events**

The investigator is responsible for notifying the sponsor within 24 hours of identifying an SAE, regardless of the presumed relationship to the investigational study drug. The SAE Form will be completed for new/initial events as well as to report follow-up information on previously reported events. Investigators are asked to report follow-up information as soon as it becomes available to ensure timely reporting to health authorities.

Please send completed SAE Forms to Vertex GPS via:

Email: [REDACTED]

Fax: [REDACTED]

For questions, contact telephone: [REDACTED]

#### **13.1.2.4 Expedited Reporting and Investigator Safety Letters**

Vertex, as study sponsor, is responsible for reporting suspected, unexpected, serious adverse reactions (SUSARs) involving the study drug(s) to all regulatory authorities, IECs, and participating investigators in accordance with ICH Guidelines and/or local regulatory requirements, as applicable. In addition, Vertex, or authorized designee, will be responsible for the submission of safety letters to central IECs.

It is the responsibility of the investigator or designee to promptly notify the local IRB/local IEC of all unexpected serious adverse drug reactions involving risk to human subjects.

## **13.2 Administrative Requirements**

### **13.2.1 Ethical Considerations**

The study will be conducted in accordance with the current ICH GCP Guidelines, which are consistent with the ethical principles founded in the Declaration of Helsinki, and in accordance with local applicable laws and regulations. The IRB/IEC will review all appropriate study documentation to safeguard the rights, safety, and well-being of the subjects. The study will only be conducted at sites where IRB/IEC approval has been obtained. The protocol, Investigator's Brochure, sample ICF, advertisements (if applicable), written information given to the subjects (including diary cards), safety updates, annual progress reports, and any revisions to these documents will be provided to the IRB/IEC by the investigator or Vertex, as allowable by local applicable laws and regulations.

### **13.2.2 Subject Information and Informed Consent**

After the study has been fully explained, written informed consent will be obtained from the subject or legal representative or guardian (if applicable), and assent will be obtained from the subject (if applicable), before study participation. The method of obtaining and documenting the informed consent and assent (if applicable) and the contents of the consent will comply with ICH GCP and all applicable laws and regulations and will be subject to approval by Vertex or its designee.

### **13.2.3 Investigator Compliance**

No modifications to the protocol will be made without the approval of both the investigator and Vertex. Changes that significantly affect the safety of the subjects, the scope of the investigation, or the scientific quality of the study (i.e., efficacy assessments) will require IRB/IEC notification before implementation, except where the modification is necessary to eliminate an apparent immediate hazard to human subjects. Vertex will submit all protocol modifications to the required regulatory authorities.

When circumstances require an immediate departure from procedures set forth in the protocol, the investigator will contact Vertex to discuss the planned course of action. If possible, contact will be made before the implementation of any changes. Any departures from the protocol will be fully documented in the source documentation and in a protocol deviation log.

### **13.2.4 Access to Records**

The investigator will make the office and/or hospital records of subjects enrolled in this study available for inspection by Vertex or its representative at the time of each monitoring visit and for audits. The records will also be available for direct inspection, verification, and copying, as required by applicable laws and regulations, by officials of the regulatory health authorities (FDA and others). The investigator will comply with applicable privacy and security laws for use and disclosure of information related to the research set forth in this protocol.

### **13.2.5 Subject Privacy**

To maintain subject confidentiality and to comply with applicable data protection and privacy laws and regulations, all data provided to Vertex, study reports, and communications relating to

the study will identify subjects by assigned subject numbers and access to subject names linked to such numbers shall be limited to the site and the study physician and shall not be disclosed to Vertex. As required by applicable laws and regulations in the countries in which the study is being conducted, the investigator will allow Vertex and/or its representatives access to all pertinent medical records to allow for the verification of data gathered and the review of the data collection process. The FDA and regulatory authorities in other jurisdictions, including the IRB/IEC, may also request access to all study records, including source documentation, for inspection.

For sites participating in the study in the US, and in accordance with the Health Insurance Portability and Accountability Act and associated regulations (“HIPAA”) an executed HIPAA authorization shall be obtained by the site from each subject (or the legal representative of the subject) before research activities may begin. Each HIPAA authorization shall comply with all HIPAA requirements including authorization allowing the site access to and use of the subject’s personally identifiable health information, authorization for the site to disclose such information to Vertex, the FDA, and other parties requiring access under the protocol, and statements as to the purpose for which such information may be used and for how long.

### **13.2.6 Record Retention**

The investigator will maintain all study records according to ICH GCP guidelines and/or applicable local regulatory requirement(s), whichever is longest, as described in the Clinical Trial Agreement. If the investigator withdraws from the responsibility of keeping the study records, custody will be transferred to a person willing to accept the responsibility and Vertex will be notified.

### **13.2.7 Study Termination**

At any time, Vertex may terminate this study in its entirety or may terminate this study at any particular site. In addition, for reasonable cause, either the investigators or their IRBs/IECs may terminate the study at their center.

Conditions that may lead to reasonable cause and warrant termination include, but are not limited to:

- Subject or investigator noncompliance
- Unsatisfactory subject enrollment
- Lack of adherence to protocol procedures
- Lack of evaluable and/or complete data
- Potentially unacceptable risk to study subjects
- Decision to modify drug development plan
- Decision by the FDA or other regulatory authority

Written notification that includes the reason for the clinical study termination is required.

### **13.2.8 End of Study**

The end of study is defined as the last scheduled visit (or contact) of the last subject in the study.

### **13.3 Data Quality Assurance**

Vertex or its designated representative will conduct a study site visit to verify the qualifications of each investigator, inspect clinical study site facilities, and inform the investigator of responsibilities and procedures for ensuring adequate and correct study documentation.

The investigator is required to prepare and maintain adequate and accurate case histories designed to record all observations and other data pertinent to the study for each study participant. Study data for each enrolled subject will be entered into a CRF by study site personnel using a secure, validated, web-based electronic data capture (EDC) application. Vertex will have read-only access to site-entered clinical data in the EDC application.

Instances of missing, discrepant, or uninterpretable data will be queried with the investigator for resolution. Any changes to study data will be made to the CRF and documented in an audit trail, which will be maintained within the clinical database.

### **13.4 Monitoring**

Monitoring and auditing procedures developed or approved by Vertex will be followed to comply with GCP guidelines. On-site checking of the data captured for the study/SAE Forms for completeness and clarity, and clarification of administrative matters will be performed.

The study will be monitored by Vertex or its designee. Monitoring will be done by personal visits from a representative of Vertex, or designee (study site monitor), who will review the data captured for the study/SAE Forms and source documents. The study site monitor will ensure that the investigation is conducted according to the protocol design and regulatory requirements.

### **13.5 Electronic Data Capture**

Vertex will provide the study sites with secure access to and training on the EDC application sufficient to permit study site personnel to enter or correct information in the CRFs on the subjects for which they are responsible.

A CRF will be completed for each enrolled study subject. It is the investigator's responsibility to ensure the accuracy, completeness, clarity, and timeliness of the data reported in the subject's CRF. Source documentation supporting the CRF data will indicate the subject's participation in the study and will document the dates and details of study procedures, AEs, other observations, and subject status.

[figure not shown]
The investigator, or designated representative, will complete the CRF as soon as possible after information is collected.

The audit trail entry will show the user's identification information and the date and time of any correction. The investigator will provide formal approval of all the information in the CRFs, including any changes made to the CRFs, to endorse the final submitted data for the subjects for whom the investigator is responsible.

Vertex will retain the CRF data and corresponding audit trails. A copy of the final archival CRF in the form of a compact disc (CD) or other electronic media will be placed in the investigator's study file.

### **13.6 Publications and Clinical Study Report**

#### **13.6.2 Clinical Study Report**

[figure not shown]
A clinical study report, written in accordance with the ICH E3 Guideline, will be submitted in accordance with local regulations.

## 15 APPENDIX 1: *CFTR* MUTATIONS

Subjects can either be homozygous or heterozygous for the *F508del* mutation. Heterozygous subjects must have *F508del* on 1 allele and a second eligible *CFTR* allele. The list below represents acceptable mutations for the second *CFTR* allele for heterozygous subjects. Most mutations were evaluated in the TEZ/IVA pivotal Phase 3 studies. However, this is a non-exhaustive list of *CFTR* mutations to be evaluated in this study. Additional mutations may be evaluated and updates to approved mutations will be communicated to investigative sites through a memorandum.

CFTR Residual Function Mutations			
2789+5G→A	D110E	D579G	D1152H
3849+10kbC→T	D110H	S945L	D1270N
3272-26A→G	R117C	S977F	E831X
711+3A→G	E193K	F1052V	A1067T
E56K	L206W	K1060T	
P67L	R352Q	R1070W	
R74W	A455E	F1074L	

During the course of study conduct, if local health authorities decline to approve, or if clinical benefit is not demonstrated for the use of TEZ/IVA for the treatment of CF in a corresponding population aged  $\geq 12$  years, pediatric subjects enrolled in Study 115 with the relevant *CFTR* genotypes may not be enrolled into the study. Subjects who are enrolled in Study 115 may be discontinued after communication to investigators and IRBs/IECs of the risks/benefits related to the safety and efficacy observed for the subset of subjects.

2 LIST OF ABBREVIATIONS

Abbreviation	Term
AE	adverse event
ALP	alkaline phosphatase
ALT	alanine aminotransferase
AST	aspartate aminotransferase
BMI	body mass index
bpm	beats per minute
CF	cystic fibrosis
CFQ-R	Cystic Fibrosis Questionnaire – Revised
CFTR	cystic fibrosis transmembrane conductance regulator
CI	confidence interval
CRF	case report form
CRO	contract research organization
DMC	data monitoring committee
ECG	electrocardiogram
eCRF	electronic case report form
F508del	CFTR gene mutation with an in-frame deletion of a phenylalanine codon corresponding to position 508 of the wild-type protein
FAS	full analysis set
FDC	VX-661 100-mg/IVA 150-mg fixed-dose tablet
FEF _{25-75%}	forced expiratory flow, midexpiratory phase
FEV ₁	forced expiratory volume in 1 second
F/F	homozygous for F508del
F/RF	heterozygous for F508del and a second allele with a residual function mutation
FVC	forced vital capacity
IVA	ivacaftor
LS means	Least squares means
LFT	liver function test
max	maximum value
MedDRA	Medical Dictionary for Regulatory Activities
min	minimum value
MMRM	mixed model repeated measure
N	number of subjects
PD	pharmacodynamic/pharmacodynamics
PK	pharmacokinetic/pharmacokinetics
ppFEV ₁	percent predicted FEV ₁
PT	preferred term
q12h	every 12 hours
QRS	Q, R, and S-wave define the QRS-complex in an ECG
QT	QT interval: The duration of ventricular depolarization and subsequent repolarization; it is measured from the beginning of the QRS complex to the end of the T wave
QTc	QT interval corrected for heart rate
QTcF	QT interval corrected for heart rate with Fridericia's correction

Abbreviation	Term
SAE	serious adverse event
SAP	Statistical Analysis Plan
SD	standard deviation
SE	standard error
SOC	system organ class
TEAE	treatment-emergent adverse event
TEZ	tezacaftor
ULN	upper limit of normal
WHODD	World Health Organization Drug Dictionary Enhanced

4 INTRODUCTION

This statistical analysis plan (SAP) Methods, which describes the planned analyses for Study VX16-661-115, is based on the most recent approved clinical study protocol (CSP), the most recent approved electronic case report form (eCRF), and the most recent approved eCRF completion guidelines.

Study VX16-661-115 is a Phase 3, double blind, parallel-group study to evaluate the efficacy and safety of tezacaftor (TEZ; VX 661) in combination with ivacaftor (IVA; VX 770) in subjects aged 6 through 11 years with cystic fibrosis (CF), homozygous or heterozygous for the *F508del-CFTR* mutation.

This SAP (Methods) documents the planned final statistical analyses of efficacy and safety endpoints defined in the VX16-661-115 study protocol. It also documents analyses for additional efficacy and safety variables not specified in the protocol.

[REDACTED]

The Vertex Biometrics Department or designee will perform the statistical analysis of the efficacy and safety data; SAS (Version 9.4 or higher) will be used to generate all statistical outputs (tables, figures, listings, and datasets). The SAP will be finalized and approved prior to the final clinical database lock and treatment unblinding for the study. If the methods in this SAP differ from the methods described in the protocol, the SAP will prevail.

5 STUDY OBJECTIVES

5.1 Primary Objective

To evaluate the efficacy of TEZ/IVA in subjects with CF aged 6 through 11 years, homozygous or heterozygous for *F508del*.

5.2 Secondary Objectives

To evaluate the safety of TEZ/IVA in subjects with CF aged 6 through 11 years, homozygous or heterozygous for *F508del*.

6 STUDY ENDPOINTS

[figure not shown]
6.1 Primary Endpoint

Absolute change in lung clearance index_{2.5} (LCI_{2.5}) from baseline through Week 8

6.2 Secondary Endpoints

- Absolute change from baseline in sweat chloride at Week 8
- Absolute change in Cystic Fibrosis Questionnaire-Revised (CFQ-R) respiratory domain score from baseline through Week 8
- Safety and tolerability as measured by adverse events (AEs), clinically significant changes in laboratory values (serum chemistry, hematology, coagulation studies, lipids, vitamin levels, and urinalysis), standard 12-lead ECGs, vital signs, pulse oximetry, serial lung function measurement (post-dose spirometry), and ophthalmologic examinations.

7 STUDY DESIGN

7.1 Overall Design

[figure not shown]
This is a Phase 3, double-blind, parallel-group study in subjects with CF aged 6 to 11 years, homozygous or heterozygous for *F508del*. Subjects will be:

- homozygous for *F508del* (F/F), or
- heterozygous for *F508del* and a second allele with a residual function mutation (F/RF).

A schematic of the study design is shown in Figure 6-1.

Figure 7-1 VX16-661-115 Study Design

Notes: Subjects who are taking commercially available CFTR modulators (Orkambi or Kalydeco) are required to washout for 28 days before the Day 1 Visit. The study will enroll a total of approximately 65 subjects, of which up to 15 subjects have an F/RF genotype. Subjects will be stratified by genotype group (F/F or F/RF) and randomized 4:1 (TEZ/IVA: blinding arm) before receiving the first dose of study drug on Day 1. The blinding treatment arm will be placebo for F/F subjects and IVA monotherapy (with TEZ-matching placebo) for F/RF subjects. Study drug dose is determined based on weight on Day 1 (<40 kg or ≥40 kg). Subjects will receive matched TEZ/IVA placebo or IVA placebo tablets as appropriate. See Table 9-2 for additional information on study drug tablets and dosing.

7.2 Sample Size and Power

The sample size of this study is driven by demonstrating that the treatment effect of TEZ/IVA excludes a maximum possible placebo effect, which is based on a within-group comparison (change from baseline in LCI_{2.5} in subjects on TEZ/IVA). If the corresponding 2-sided 95% CI of the change from baseline in LCI_{2.5} in subjects on TEZ/IVA excludes the pre-defined maximum possible placebo effect, it will be considered that the study has achieved its primary objective.

A placebo effect is not expected with LCI, because clinical data from other Vertex CFTR modulator studies consistently demonstrated a worsening of lung function (i.e., an increase from baseline in LCI) in the absence of CFTR modulator treatment. Study VX14-809-109 (Study 809-109) evaluated treatment with LUM/IVA in F/F subjects aged 6 through 11 years using change from baseline in LCI as the primary efficacy endpoint and provided the most relevant clinical LCI data available in the younger age group of CF subjects. In Study 809-

109, the placebo group had a mean worsening in LCI_{2.5} of 0.08 units with an SD of 1.41 (higher numbers indicate a worsening of an LCI measurement); the one-sided 90% lower bound was -0.10 and is used as an estimate for the pre-defined maximum possible placebo effect for Study 115.

Accounting for a 10% dropout rate, approximately 40 subjects in the TEZ/IVA group will provide at least 90% power to exclude -0.10 if the true mean change is -0.9 with an SD of 1.41 using a two-sided alpha of 0.05. The current estimate of the maximum possible placebo effect is based on Study 809-109 placebo data in pediatric F/F subjects with CF.

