**Secondary Endpoints**

- Absolute change from baseline in sweat chloride at Week 8
- Absolute change in Cystic Fibrosis Questionnaire-Revised (CFQ-R) respiratory domain score from baseline through Week 8
- Safety and tolerability as measured by adverse events (AEs), clinically significant changes in laboratory values (serum chemistry, hematology, coagulation studies, lipids, vitamin levels, and urinalysis), standard 12-lead ECGs, vital signs, pulse oximetry, serial lung function measurement, and ophthalmologic examinations.

Number of Subjects	Approximately 65 subjects total, of which up to 15 subjects are heterozygous for F508del and a second CFTR allele that results in residual function (F/RF)
Study Population	Male and female subjects aged 6 through 11 years with CF who are F/F or F/RF
Investigational Drug	
Active substance: TEZ and IVA
 
Activity: CFTR corrector and potentiator (increased Cl secretion)
 
Strength and route of administration: TEZ 50 mg/IVA 75 mg fixed-dose combination (FDC) tablet or TEZ 100 mg/IVA 150 mg FDC tablet; oral administration
 
Active substance: IVA
 
Activity: CFTR potentiator (increased Cl secretion)
 
Strength and route of administration: IVA 75- or 150-mg tablet; oral administration
 
Active substance: Not applicable
 
Activity: Placebo
 
Strength and route of administration: 0-mg matching placebo tablets for oral administration

Study Duration	Each subject will participate in the study for 16 weeks: 4-week Screening Period, 8-week Treatment Period, and 4-week Safety Follow-up Period.

[figure not shown]

**Study Design** This is a Phase 3, double-blind, parallel-group study in subjects with CF who are homozygous or heterozygous for the *F508del-CFTR* mutation. The study is designed to evaluate the efficacy and safety of TEZ/IVA treatment in pediatric subjects aged 6 through 11 years.

[figure not shown]
Subjects will be stratified by genotype group (F/F or F/RF) and randomized 4:1 (TEZ/IVA: blinding arm) and treated as shown in Figure 2-1. The blinding arm will be placebo for F/F subjects and IVA monotherapy (with TEZ-matching placebo) for F/RF subjects.

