### 12.3 Statistical Analysis

The Vertex Biometrics Department or designee will analyze the safety and efficacy data.

The primary objective of this study is efficacy. The secondary objective is safety. This section summarizes the statistical analysis of efficacy and safety data. Methodological and related details (e.g., missing data) will be provided in the SAP.

The primary efficacy endpoint is the absolute change in  $LCI_{2.5}$  from baseline through Week 8. The objective of primary efficacy endpoint analysis is to demonstrate that the mean absolute change from baseline in  $LCI_{2.5}$  through Week 8 for subjects on TEZ/IVA excludes a pre-defined maximum placebo effect. The primary analysis of the primary efficacy endpoint will be based on a mixed-effects model for repeated measures (MMRM) with  $LCI_{2.5}$  at each time point as the outcome variable. The estimated mean change from baseline through Week 8 in  $LCI_{2.5}$  for subjects on TEZ/IVA along with the corresponding 95% CI will be provided. If the upper bound of the 95% CI is below the pre-defined maximum possible placebo effect, it will be interpreted as sufficient evidence to achieve the primary efficacy objective.

The study plans to enroll approximately 50 F/F subjects and up to 15 F/RF subjects.

A placebo group of F/F subjects and an IVA mono group of F/RF subjects will be included in this study. The main purpose is to preserve blinding, so that subjects and investigators do not assume a subject is receiving TEZ/IVA, which could introduce bias into the results. Descriptive statistics such as mean and SD will be provided for change from baseline in  $LCI_{2.5}$  at each post-baseline visit for homozygous subjects in the placebo group.

The target enrollment by genotype and treatment group is provided in the Table 12-1.

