9.3.1 Analysis of the Primary Efficacy Variable

The primary efficacy endpoint is the absolute change in $LCI_{2.5}$ from baseline through Week 8. The objective of the primary efficacy endpoint analysis is to demonstrate that the mean absolute change from baseline in $LCI_{2.5}$ through Week 8 excludes a pre-defined maximum placebo effect in subjects in the TEZ/IVA group.

The primary analysis will be performed using a restricted maximum likelihood (REML)-based mixed-effect model for repeated measures (MMRM) for the subjects in the TEZ/IVA treatment group in the FAS population. The model will include absolute change from baseline in $LCI_{2.5}$ (including all measurements up to Week 8 [inclusive], both on treatment measurements and measurements after treatment discontinuation) as the dependent variable, and visit (as a class variable) as a fixed effect, with adjustment for mutation group based on the second *CFTR* allele (F/F and F/RF) and baseline $LCI_{2.5}$ (continuous) value as covariates, and subject as a random effect. An unconstructed covariance structure will be used to model the within-subject errors. If the model fails to converge, a compound symmetry covariance structure will be considered. The degrees of freedom of the denominator will be approximated by the Kenward-Roger's method².

The primary results obtained from the model will be the estimated average treatment effect through Week 8 in $LCI_{2.5}$ for subjects on TEZ/IVA. The corresponding LS mean, standard error (SE), 95% CI, and *p*-value will be provided. If the upper bound of the 95% CI is below the pre-defined maximum possible placebo effect, which was specified in the protocol, it will be considered that the study has achieved its primary objective. Summary statistics for change from baseline in $LCI_{2.5}$ through Week 8, and at each visit will also be provided for subjects in the TEZ/IVA treatment group by mutation groups and overall.

For F/F subjects in the placebo treatment group, summary statistics will be provided for change from baseline in LCI_{2.5} through Week 8, and at each visit.

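### The -0.10 threshold rests on F/F placebo data alone but is tested on a pooled F/F and F/RF mean, so pooled success does not by itself show that F/F subjects exceed the F/F placebo allowance.

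*SAP*

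**What the plan says.** SAP 7.2 explains the threshold. It starts from the placebo result of Study 809-109: "the placebo group had a mean worsening in LCI_{2.5} of 0.08 units with an SD of 1.41". The success limit is then taken from the edge of that estimate: "the one-sided 90% lower bound was -0.10 and is used as an estimate for the pre-defined maximum possible placebo effect for Study 115". The source population is named: "The current estimate of the maximum possible placebo effect is based on Study 809-109 placebo data in pediatric F/F subjects with CF". Protocol 12.1 gives the same derivation. It also allows the value to be updated if more relevant data appear; the SAP keeps -0.10.

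The sample size statement reads "Accounting for a 10% dropout rate, approximately 40 subjects in the TEZ/IVA group will provide at least 90% power to exclude -0.10". Behind that figure the SAP assumes a change of -0.9, SD 1.41 and a two-sided 5% level.

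Protocol 12.3 says: "The study plans to enroll approximately 50 F/F subjects and up to 15 F/RF subjects". Table 12-1 splits the TEZ/IVA arm into 40 F/F and 12 F/RF. On controls, the Protocol Synopsis (Study Design) says: "The blinding arm will be placebo for F/F subjects and IVA monotherapy (with TEZ-matching placebo) for F/RF subjects".

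The primary model in SAP 9.3.1 is fitted "for the subjects in the TEZ/IVA treatment group in the FAS population", with both genotypes together and adjustment for mutation group. Success means that the upper 95% limit of the one overall estimate lies below -0.10. Results by mutation group are summary statistics only. Neither document says how the overall least-squares mean weights the two genotypes.

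**The concern.** The threshold stands in for a concurrent placebo comparison, so its meaning depends on the population that produced it. That population is F/F. The documents give no untreated F/RF reference, and the F/RF control arm receives ivacaftor.

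The 40 subjects in the power statement match the F/F TEZ/IVA count in Table 12-1, yet the test also takes in up to 12 F/RF subjects. An F/RF response can move the pooled mean past -0.10 while the F/F mean stays at or above it. No planned model estimate or interval compares F/F with the benchmark drawn from F/F. At stake is what may be said about the largest genotype group, and about the only one the threshold describes, after a positive result.

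**Working it through.** **Inputs.** From SAP 7.2: SD 1.41, true change -0.9, threshold -0.10, two-sided alpha 0.05, 10% dropout, historical placebo mean +0.08. From Table 12-1: 40 F/F and 12 F/RF on TEZ/IVA, so 40 × 0.9 = 36 and 12 × 0.9 = 10.8 evaluable. Assumptions: the same SD in both genotypes, SD 1.41 applies to the average through Week 8, the baseline covariate is ignored, and F/RF changes by -0.9.

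**1. The plan's own power.** SE = 1.41/√36 = 0.235. Noncentrality = (-0.9 + 0.10)/0.235 = -3.40. The critical t on 35 df is 2.030. Noncentral-t power is 91.1% (normal approximation 92.6%), so the stated figure of at least 90% is reproduced.

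**2. The pooled test.** With F/RF weight w:

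- pooled mean = (1-w)·μ(F/F) + w·μ(F/RF)
- SE = 1.41·√[(1-w)²/36 + w²/10.8]
- success if the estimate is below -0.10 - 2.014·SE (df 46.8 - 2)

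Subject weighting: w = 10.8/46.8 = 0.231, SE 0.206, cut-off -0.515. Equal weighting: w = 0.5, SE 0.245, cut-off -0.593.

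Chance of pooled success with F/RF at -0.9:

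| True F/F change | Pooled mean, subject-weighted | Success | Pooled mean, equal-weighted | Success |
|---|---|---|---|---|
| -0.10 | -0.285 | 13.9% | -0.50 | 36.0% |
| 0 | -0.208 | 7.4% | -0.45 | 28.8% |
| +0.08 | -0.146 | 4.1% | -0.41 | 23.6% |

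A 40,000-run simulation with 36 and 11 subjects agreed for the cases it covered: 13.9% and 36.5% at F/F -0.10, and 7.6% and 29.4% at F/F 0.

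If the observed F/F mean is 0, the observed F/RF mean must be below -0.515/0.231 = -2.23 with subject weights, or -0.593/0.5 = -1.19 with equal weights.

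**3. Half the F/RF enrolment** (5.4 evaluable), F/F at -0.10. Subject weighting: w = 5.4/41.4 = 0.130, SE 0.219, success 6.7%. Equal weighting: SE 0.325, success 22%.

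**4. Power of the pooled test with both genotypes at -0.9.** Subject weighting: -0.8/0.206 = -3.88, power 96.7%. Equal weighting: -0.8/0.245 = -3.27, power 89.3% (89.7% if 10.8 is rounded to 11; 92.2% with 40 and 12 and no dropout).

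**5. F/F alone, n = 36.** The chance of passing is 2.5% at a true change of -0.10, about 0.9% at 0, and 91.1% at -0.9. The 95% half-width is 2.030 × 0.235 = 0.477, against 2.014 × 0.206 = 0.415 for the subject-weighted pooled mean. F/RF alone, with 11 to 12 subjects, would have about 40% to 43% power.

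**The case against.** The stated primary objective covers subjects homozygous or heterozygous for *F508del*, and the success rule concerns the mean of the whole TEZ/IVA group. No section promises a separate F/F conclusion. A reader might compare the table with 2.5% and infer an inflated type I error. The documents do not support that: in every scenario shown the true pooled mean is below -0.10, so rejecting the pooled null is correct. The percentages are power for the planned hypothesis, read against a question the plan does not test. This part of the objection stands in full.

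A reader might also infer that F/RF subjects can readily carry the trial when F/F has no effect. With subject weighting the figures are 7.4% at F/F 0 and 4.1% at the historical +0.08. The F/F value of -0.10 is already 0.18 better than that historical mean. The large figures need equal weighting, which is the usual default for a class variable but is not stated in the SAP. They also assume that -0.9 holds in F/RF and that F/RF enrolment is full, although 15 is a ceiling.

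The threshold's source is disclosed and defended as the most relevant data for this age group. The planned by-genotype summaries include n, mean and SD, so an unadjusted F/F interval could be computed and a null F/F result would be visible. That mitigates the problem, but it leaves the reading of an F/F result to be settled after unblinding.

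**Conclusion.** The concern holds as a limit on interpretation. The planned pooled test is valid for the pooled mean, but passing it does not show that F/F subjects exceed the allowance taken from F/F placebo data.

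The size depends mainly on a choice the SAP leaves open. With F/RF at -0.9, pooled success occurs in about 4% to 14% of trials under subject weighting and 24% to 36% under equal weighting, as the true F/F change runs from +0.08 to -0.10. With half the F/RF enrolment and F/F at -0.10, it is about 7% and 22%.

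The figures also rest on SD 1.41. If the SD were 1.0 (an assumption), F/F at 0 and F/RF at -0.9 would give 11% to 12% under subject weighting and 51% to 55% under equal weighting. The F/RF effect is unknown; -0.9 is the plan's overall assumption carried over to that group.

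**What to change.** In SAP 9.3.1:

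1. Keep the pooled primary analysis and state that its least-squares mean uses observed genotype proportions (for example, observed margins). Equal weighting would give about 11 F/RF subjects half the estimate and lower power to about 89% when both genotypes are at -0.9, just under the stated 90%.
2. Pre-specify, as supportive, the same repeated-measures model in F/F TEZ/IVA subjects alone, without the mutation-group term. Report its least-squares mean and 95% interval against -0.10, and base any F/F-specific statement on it.
3. Report the F/RF estimate and interval descriptively, without applying the F/F threshold.

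No further subjects are needed, because the planned 40 F/F subjects already support item 2 at the stated power. The cost is one extra model, a few sentences, and an F/F interval wider than the pooled one (half-width about 0.48 against 0.42).
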